2.7.3 Handling of missing values/censoring/discontinuations

Time to second progression (PFS2)

The rules for censoring and event for PFS2 are summarized in [Section 2.7.1](#).

Overall Survival (OS)

If a patient is not known to have died at the time of analysis cut-off, then OS will be censored at the date of last known patient was alive, i.e., last contact date (see [Table 2.1-2](#)).

2.8 Safety analyses

For the treatment phase, all safety analyses will be based on the safety set. Separate safety analyses will be performed for patients during the crossover and re-treatment phase as appropriate.

2.8.1 Adverse events (AEs)

All adverse events (AEs), whether or not spontaneously reported by the patient, will be recorded starting from the signing of the ICF until the end of the randomized period/cross-over period/re-treatment period. During the Follow up Phase, only related serious adverse events and adverse events of special interest will be recorded, except for secondary hematological malignancies which will be recorded irrespective of relationship to Lutathera, Octreotide, and amino acid. The data provides information regarding relatedness to Lutathera, Octreotide and amino acid.

AEs that started or worsened during the on-treatment period (including randomized treatment, cross-over and re-treatment periods as defined in [Section 2.1.1.10](#)) is defined as treatment-emergent AEs (TEAE). The primary AE summaries will focus on all treatment-emergent AEs in the randomized treatment period that started or worsened during the randomized treatment

period, defined as from date of first administration of study treatment to 30 days after the date of the last actual administration of any study treatment in the randomized period before cross-over or retreatment. However, selected AE summaries will also be generated for cross-over and re-treatment periods separately. All AEs collected in the eCRF page will be listed along with the information collected e.g., AE relationship to study drug, AE outcome etc. In addition, each AE record in the listings will be flagged for its study period based on the start date.

AEs will be summarized by number and percentage of subjects having at least one AE, having at least one AE in each primary system organ class (SOC) and for each preferred term (PT) using MedDRA coding. A subject with multiple occurrences of an AE will be counted only once in the respective AE category. A subject with multiple CTCAE grades for the same preferred term will be summarized under the maximum CTCAE grade recorded for the event. AE with missing CTCAE grade will be included in the 'All grades' column of the summary tables.

In AE summaries, the primary SOC will be presented alphabetically and the PT will be sorted within primary SOC in descending frequency. For randomized period AE summaries, the sort order for the PT will be based on their frequency in the investigational arm.

The following AE summaries will be produced by treatment arm; overview of AEs and deaths (number and % of subjects who died, with any AE, any SAE, any dose reductions/interruptions etc), AEs by SOC and PT, summarized by relationship (all AEs and AEs related to study treatment), seriousness (SAEs and non-SAEs), leading to treatment discontinuation, leading to dose reduction/interruption, requiring additional therapy and leading to death (both related to study treatment and irrespective of study treatment). In addition, a summary of SAEs with number of occurrences will be produced (an occurrence is defined as >1 day between start and prior end date of record of same preferred term).

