3.2 Treatment Phase

During the Treatment Phase, patients will be followed according to the assessments schedule in Table 8-3, and Table 8-4. Objective tumor response will be assessed at W16 \pm 1, W24 \pm 1 and then every 12 \pm 1 weeks from the randomization date, according to RECIST 1.1 criteria (central + local assessment up to first progression, then only local assessment).

Duration of the Treatment Phase:

• Before the PFS primary analysis:

The Treatment Phase is not fixed and the patients who are randomized should continue to receive the study treatments until progression or death (patients randomized in the Lutathera arm, will continue octreotide long-acting 30 mg injections after the completion of the 4 Lutathera treatments until progression or death; patients randomized in the octreotide long-acting arm will continue octreotide long-acting 60 mg injections until progression or death).

• After the PFS primary analysis:

The Treatment Phase becomes fixed and will stop at week 72 (patients randomized in the Lutathera arm, will continue octreotide long-acting 30 mg injections after the completion of the 4 Lutathera treatments until week 72 or earlier in case of progression or death; patients randomized in the octreotide long-acting arm will continue octreotide long-acting 60 mg injections until week 72 or earlier in case of progression or death).

In other words, before the PFS primary analysis (i.e. 99 evaluable and centrally confirmed disease progressions or death events), patients continue the Treatment Phase until progression; after the PFS primary analysis, the Treatment Phase duration is limited to 72 weeks.

At any time during the study (before or after the PFS primary analysis) any progressive patient (based on central imaging assessment) immediately ceases the Treatment Phase and proceeds to the Follow-up Phase (Table 8-3 and Table 8-4). If a patient discontinues Lutathera before centrally confirmed disease progression, the patient should be followed with tumor assessments as per initial CT/MRI schedule until centrally confirmed disease progression.

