2.1.1.10 Definition of treatment periods used in analyses

Pre-treatment period:

From day of patient's informed consent to the day before first administration of study treatment in the treatment phase.

Randomized treatment period:

An on-treatment assessment/event during randomized treatment period is defined as any assessment/event in the following time intervals:

- [date of first administration of study treatment, minimum (date of last administration of study treatment in randomized treatment phase + 30 days, 1st injection of Lutathera in extension phase – 1 day)]

Between treatments period:

This period starts from the end of randomized treatment period as defined above to the day before the 1st injection of Lutathera in the extension (cross-over/re-treatment) treatment period. It is not applicable for patients without cross-over/re-treatment and for those who start the cross-over/re-treatment period less than 30 days from the last administration of study treatment in the randomized treatment period.

Cross-over or re-treatment period:

An assessment/event during the cross-over or re-treatment period is defined as any assessment/event in the following time interval:

- [date of first administration (or re-treatment) of Lutathera, date of last administration of study treatment + 30 days]

Note: the calculation of study treatment duration will use different rules as specified in [Section 2.4.1.1](#).

Due to the limited and immature data in cross-over/re-treatment period, efficacy analyses for this period or the corresponding subset will not be generated at the time of primary PFS analysis. Instead, they will be summarized in the future for study update and publication use. Nevertheless, selected key safety output will be generated to include this period for the completeness of safety review.

Note: The date of first administration of study treatment and the date of last administration of study treatment are defined in [Section 2.1.1.4](#) and [Section 2.1.1.5](#), respectively.

Post-treatment follow up period:

The post treatment period is defined as the following:

- For patients who do not receive either cross-over or re-treatment: Post-treatment period starts at the 31st day after the last study treatment administration in the randomized Treatment Phase (i.e., the day after end of on-treatment period) to the End of Study.

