2.13 Interim analysis

There will be no interim analysis with inferential intent. But, at the time of the PFS primary analysis, an estimate of overall survival will be calculated in terms of hazard ratio (point estimate) and 95% confidence interval. Furthermore, a presentation of safety will be prepared including data from the time period up the interim.

3 Sample size calculation

The sample size calculation is based on the primary variable PFS. Assuming a median PFS in the control arm (High Dose octreotide long-acting (60 mg)) of approximately 15 months, it is hypothesized that treatment with Lutathera added to standard dose octreotide long-acting will result in a 50% reduction in the hazard rate (corresponding to an increase in median PFS from 15 months to 30 months).

To ensure 90% power to test the null hypothesis: PFS hazard ratio = 1, versus the specific alternative hypothesis: PFS hazard ratio = 0.50, it is calculated that a total of 99 PFS events need to be observed. This calculation assumes analysis by a one-sided log-rank test at the overall 2.5% level of significance, patients randomized to the two treatment groups in a 2:1 ratio. Assuming that enrolment will continue for approximately 22.2 months at a rate of 10 patients per month and a 15% dropout rate by the time of the final PFS analysis, a total of 222 patients (148 for Lutathera arm and 74 for the control arm) will need to be randomized to observe the targeted 99 PFS events at about 12.8 months after the randomization date of the last patient, i.e., 35 months after the randomization date of the first patient. If the final analysis is performed when the targeted 99 PFS events are observed, the observed hazard ratio will have to be < 0.658 which corresponds to a difference in median PFS of 7.8 months to declare statistical significance.

These calculations were made using the software package East 6.4.

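### Outside the AESI groups, adverse events are compared between arms only as crude percentages, although the plan's own PFS assumptions imply about 26% longer time on treatment with Lutathera

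*SAP*

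**What the plan says.** - **Summary measure.** SAP Section 2.8.1: "AEs will be summarized by number and percentage of subjects having at least one AE", then by system organ class and preferred term. The tables by arm for SAEs, AEs leading to discontinuation and AEs leading to dose reduction or interruption are of the same kind.
- **Window.** The main AE summaries cover the randomized treatment period. SAP Section 2.1.1.10 ends it at the "minimum (date of last administration of study treatment in randomized treatment phase + 30 days", or the day before the first extension-phase Lutathera dose if that is earlier.
- **Treatment duration.** Protocol Section 3.2, for the time before the primary PFS analysis: "The Treatment Phase is not fixed and the patients who are randomized should continue to receive the study treatments until progression or death". In follow-up, only related SAEs and related AESIs are recorded, plus secondary hematological malignancies whatever their cause (Protocol Section 8.5.1).
- **Expected effect.** SAP Section 3 assumes a halved hazard, "corresponding to an increase in median PFS from 15 months to 30 months".
- **Purpose.** SAP Section 2.7 lists the rate of AEs and laboratory toxicities among the other secondary objectives on which the two arms are to be compared.
- **Time-aware elements.** SAP Section 2.8.1.1 plans Kaplan-Meier time to first occurrence for the AESI categories. SAP Section 2.4.1.1 summarizes duration of exposure by treatment group.

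**The concern.** A crude percentage depends on both how often an event occurs and how long patients are watched. Here the length of observation depends on the primary outcome: if Lutathera delays progression, its patients stay longer in the period in which AEs are counted. Part of any between-arm difference in crude AE percentages is then a by-product of efficacy.

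This works in two directions. A background event unrelated to either drug will look more frequent on Lutathera. An event that is truly more frequent per month on control can look equal. The crude table also cannot show whether an excess arises during the Lutathera cycles or only from longer treatment. For AEs, SAEs and discontinuations outside the AESI groups, no other planned table by arm separates these explanations.

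**Working it through.** **Inputs from SAP Section 3.** Control median PFS 15 months ("Assuming a median PFS in the control arm (High Dose octreotide long-acting (60 mg)) of approximately 15 months"); Lutathera median 30 months; 148 and 74 patients; accrual over 22.2 months; 15% dropout by the PFS analysis; analysis 35 months after first randomization.

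**Assumptions of this check, not in the documents.** Exponential PFS and dropout, uniform accrual, treatment stopping at progression or dropout, and an AE with constant monthly rate r, equal in both arms.

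**Step 1: reproduce the plan's figures.**
- Events = (1.960 + 1.282)² / [(2/9)(ln 0.5)²] = 98.4, rounded up to 99, as stated.
- Critical hazard ratio = exp(−1.96/√(99 × 2/9)) = 0.658, as stated; 15/0.658 − 15 = 7.8 months, as stated.
- Hazards are ln 2/15 = 0.0462 (control) and ln 2/30 = 0.0231 (Lutathera) per month. A dropout hazard η = 0.0099 per month gives 15% dropout by month 35 and 99.4 expected events, matching the plan's timing.

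**Step 2: mean time on treatment at month 35.** With h = PFS hazard + η and entry time a uniform on 0 to 22.2, average (1 − exp(−h(35 − a)))/h over a.
- Control 12.8 months, Lutathera 16.2 months, ratio 1.26.

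**Step 3: crude percentage with at least one AE.** Let X be the earliest of progression, dropout and cut-off. With the 30-day tail taken as one month, the share is 1 − exp(−r) × E[exp(−rX)].

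| Assumed rate per month, both arms | Lutathera | Control | Ratio |
|---|---|---|---|
| 1% | 15.5% | 12.6% | 1.23 |
| 2% | 27.9% | 23.0% | 1.21 |
| 3% | 38.0% | 31.8% | 1.20 |
| 5% | 53.1% | 45.3% | 1.17 |
| 10% | 73.6% | 65.3% | 1.13 |
| 30% | 92.5% | 88.2% | 1.05 |

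At 1 to 5% per month the gap is about 3 to 8 percentage points.

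**Step 4: how far the result moves.**
- Without the 30-day tail: 1.25 to 1.20 at 1 to 5% per month.
- Other readings of the 15% dropout (none; 15% per patient over 35 months; 15% per year), with or without the tail: 1.17 to 1.26.
- True hazard ratio 0.658 instead of 0.50, with 15% dropout per patient over 35 months (η = 0.0046): 1.12 to 1.15.
- AE risk confined to the first 32 weeks: about 1.05 to 1.06. Risk falling to a quarter after 32 weeks, from initial rates of 5 to 20% per month: 1.07 to 1.12.

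**Step 5: masking.** If the true rate were 2.5% per month on control and 2.0% on Lutathera, a 25% excess on control, the crude percentages would be 27.6% and 27.9%.

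**Step 6: what the added tables would show for the 2% case.**
- Exposure-adjusted rate: 0.02 × 12 × 100 = 24 per 100 patient-years in both arms, ratio 1.00.
- Crude table limited to the first 32 weeks: 12.6% against 11.9%, ratio 1.06.

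**The case against.** **What stands.**
- The plan assumes nothing about AE rates, so the size rests on an assumed constant, equal rate. Lutathera is given as four infusions about 8 weeks apart. Early clustering of its toxicity is plausible, and the distortion is then small.
- The AE comparison is descriptive. SAP Table 1.2-1 words the objective as evaluating safety and tolerability, and no test or error rate is affected.
- Exposure is tabulated by arm, so a reader can see the imbalance, and the main identified risks have Kaplan-Meier curves.
- The SAP's change history records that an exposure-adjusted AE analysis was taken out before database lock. That points to a choice, not an oversight, and is no error in itself.
- Constant-rate adjustment spreads early toxicity over the longer Lutathera follow-up and can flatter that arm.

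**What does not.** An exposure summary shows the imbalance but not what it does to any given event. The AESI curves do not cover other AEs, SAEs or discontinuations. Nor is the distortion only conservative against Lutathera, since Step 5 shows it can hide a control-arm excess.

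**Stronger readings that a reader might infer, and that the documents do not support.**
- That AE observation is twice as long on Lutathera because median PFS doubles. The cut-off truncates follow-up, and the ratio is 1.26.
- That octreotide-related events would appear falsely in excess on Lutathera. Planned octreotide intensity is 15 mg/week on control against 3.75 and then 7.5 mg/week on Lutathera (SAP Section 2.4.1.3), so an equal-rate calculation does not apply to them.
- That harms should be read only from adjusted tables. Given the dilution of early toxicity, that would replace one distortion with another.

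**Conclusion.** The point holds as a gap in the descriptive safety presentation, not as an error that threatens the trial's conclusions. For AEs outside the AESI groups, crude percentages by arm will partly reflect time on treatment, which the design itself expects to differ by a factor of 1.26 at the primary analysis. Under an equal constant rate of 1 to 5% per month, the crude percentage is inflated on Lutathera by a factor of 1.17 to 1.23. That is a conditional figure: about 1.24 for rare events, about 1.05 for very common or early events, and about 1.12 to 1.15 if the true hazard ratio is 0.658. Stopping treatment for reasons other than progression or dropout was not modelled and could move the ratio either way. Inexpensive supplementary tables would remove most of the distortion.

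**What to change.** In SAP Section 2.8.1, keep the crude tables as the primary presentation and add two supplementary descriptive outputs by arm for the randomized treatment period:

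1. Exposure-adjusted incidence rates, as patients with an event per 100 patient-years, with time counted to first event or end of the period, for TEAEs, SAEs, Grade 3 or higher AEs and AEs leading to discontinuation.
2. A crude table limited to a common window from first dose, for example the first 32 weeks.

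State that both are interpreted together with the crude tables and the exposure summary, not in place of them.

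The cost is a few extra outputs from AE dates and dosing records already held, with no effect on alpha, efficacy analyses or trial conduct. The drawback is that constant-rate adjustment can dilute early Lutathera toxicity; the common-window table is there to show it.

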2.8.1.1 Adverse events of special interest / grouping of AEs

An adverse event of special interest (AESI) is a grouping of adverse events that are of scientific and medical concern specific to Lutathera.

Certain AESIs in this study are flagged in the eCRF by the investigator within the adverse event form, and the categories for Lutathera are included in [Table 2.8-1](#) below:

Table 2.8-1 Adverse events of special interest

AESI categories	Special consideration regarding grade
Immediate hematotoxicities	For Haematopoietic thrombocytopenia (SMQ), only include Grade >=2; for others only include Grade >=3.
Cardiovascular and Electrolyte Disorder	Only include Grade >=3.
Secondary hematological malignancies	
Nephrotoxicities	

To be conservative and align within the Lutathera NET program, these groupings are re-derived using MedDRA terms, SMQs (standardized MedDRA queries), HGLTs (high level group terms), HLT (high level terms) or PT. Customized SMQs (Novartis MedDRA queries, NMQ) may also be used. A NMQ is a customized group of search terms which defines a medical concept for which there is no official SMQ available or the available SMQ does not completely fit the need. It may include a combination of single terms and/or an existing SMQ, narrow or broad.

The grouping of AEs in AESI according to project standards will be specified in the electronic Case Retrieval Sheet (eCRS) and may be regularly updated. In addition, further rules regarding grade (see [Table 2.8-1](#)) will be implemented for the groupings of Hematotoxicities, Cardiovascular and electrolyte disorder.

Data analysis of AESIs

The re-derived AESI groupings using eCRS will be used in the analyses. Summaries of AESIs will be provided by treatment arm (specifying grade, seriousness, relationship, leading to treatment discontinuation, leading to dose reduction/interruption, death etc.). Separate summaries for AESIs will be provided for the randomized treatment period, and the overall study period. An analysis of time to first occurrence of each type of AESIs will be performed for the randomized treatment period. In addition, time to first occurrence will also be performed for long-term AESIs for patients who have been treated with Lutathera (see below for more details).

Time to first occurrence in the randomized treatment period

Median time to first occurrence and 95% CI will be provided based on the Kaplan-Meier method. The event free rate at selected timepoints will be also estimated with 95% CI. In addition, Kaplan-Meier plots will be generated.

Time to first occurrence of AESI is defined as the time from the start of treatment to the start date of the first occurrence of any AE under the specific AESI in the randomized treatment period, i.e. time in days is calculated as (start date of first occurrence in the randomized treatment period) – (date of first dose of study treatment) +1. A participant will be censored if:

- The participant did not report any post-baseline AESI on or before the analysis cut-off date in the randomized treatment period.
- The participant discontinued randomized treatment without reporting the specific AESI in the randomized treatment period.
- The participant died without reporting the specific AESI in the randomized treatment period.
- The participant received a new anticancer therapy before reporting the specific AESI in the randomized treatment period.

The censoring date will be the earliest of the following dates: end date in the randomized treatment period, analysis cut-off, new anti-cancer therapy start date, death date and last contact date.

In addition, the median time to first occurrence for the subset of participants who experienced the event of interest will be calculated. Simple descriptive statistics, median, min and max as well as 25th percentile and 75th percentile, will be presented.

Time to first occurrence during the study

For long-term AESIs that can potentially occur after study treatment during follow-up, similar analysis as above will be repeated to consider all study periods, including randomized treatment period and any subsequent periods during the study. Such AESI includes secondary hematological malignancies and nephrotoxicity. This analysis is only for patients who have been treated with Lutathera, i.e., patients who were treated in the Lutathera arm and patients who did cross-over from the control arm. For cross-over patients, the time to first occurrence of AESI is counted from the start of cross-over to Lutathera instead of the randomized treatment and it will be summarized separately from the Lutathera arm.

Events/censoring rules are same except that all assessments in the study will be used regardless of study periods. The censoring date will be the earliest of the following dates: analysis cut-off, death date and last contact date in the study.

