10.1.5 Adverse Events of Special Interest

AESI are defined as events (serious or non-serious) which are ones of scientific and medical concern specific to the Sponsor's product or program, for which ongoing monitoring and rapid

communication by the Investigator to the Sponsor is appropriate. Such events require further investigation in order to characterize and understand them.

AESI are defined based on the NETTER-1 study established AESI list as well as on the basis of an ongoing review of the safety data collected during Lutathera clinical programs and post marketing.

These potential risks deserve special attention even if they do not fulfill any of the seriousness criteria. AESI occurring in patients enrolled in both arms should be reported to the Sponsor for safety analysis following the reporting procedure and timelines for SAEs. During the treatment phase, all AESI need to be reported to the Sponsor irrespective of causality. During the follow-up phase, AESI need to be reported only if considered related to the study treatment except for all secondary hematological malignancies which need to be reported as AESI irrespective of causality.

The following AESI categories representing main risks of Lutathera and amino acid treatment are listed in Table 10-1.

Table 10-1. Adverse events of special interest

AESI categories
Hematotoxicity
Secondary hematological malignancies
Nephrotoxicityg
Cardiovascular and electrolyte disorders

Hematotoxicity: The main critical organ of Lutathera treatment is the bone marrow. Significant hematotoxicity, defined as Grade 2 or higher thrombocytopenia, or Grade 3 or 4 of anaemia, leuko-/neutropenia are considered dose-modifying toxicities in the study and must be reported as AESI when not strictly fulfilling the criteria of serious adverse events. Haematological toxicities regardless of severity must be reported as AESI if accompanied by clinical consequences, i.e., infections in the presence of leuko-/neutro-/lymphopenia, hemorrhages / purpuric lesions under thrombocytopenia that is not explained by another coagulation disorder, dyspnea / fatigue in the presence of anaemia not otherwise explained by the underlying carcinoid syndrome or other co-morbidity.

Secondary haematological malignancies: any secondary hematological malignancies, irrespective of causality, including MDS and acute myeloid leukemia, should be reported in every case, as AESI/SAE.

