Nephrotoxicity: Since Lutathera is cleared through the kidneys and reabsorbed by the kidneys, the kidneys have always been considered the "critical organs". An infusion of sterile amino acid is used for kidneys protection by inhibition of tubular reabsorption of Lutathera. Pursuant to these risk minimization efforts and in addition to the criteria of dose-modifying toxicities and criteria of inclusion (at baseline and before subsequent treatments) pertinent to renal function measurements, renal and urinary tract toxicities are considered AESI. Investigators must report as AESI renal toxicities, including renal failure (ranging from significantly reduced measured or estimated creatinine clearance to clinically overt renal failure other than that of obvious non-

IMP-induced origin), suspected radiation nephropathy of any type, such as radiation-induced thrombotic microangiopathy (manifested with, e.g., proteinuria, hypertension, edema, anaemia, decrease serum haptoglobin), or general symptoms and signs of acute radiation toxicity (e.g., increased frequency and urgency of urination, nocturia, dysuria, bladder spasm, bladder obstruction, genitourinary ulceration or necrosis).

Cardiovascular and electrolyte disorders: All clinically significant changes in blood pressure, heart rate, and electrocardiogram parameters must be reported as AESI if they occur within reasonable propinquity of Lutathera and/or amino acid administration in the judgment of the Investigator. Likewise, clinically manifest and/or consequences of hypo-/hypertension, arrhythmias, cardiac conduction disturbances, and other cardiac pathologies evidenced by objective findings / changes on electrocardiogram or echocardiography should also be considered for AESI reporting. In addition, any clinically significant event of hyperkalemia or hypokalemia must be reported as AESI.

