The number (and proportion) of subjects with AESI/related to identified and potential risks (see Section 10.1) will be summarized by treatment.

A subject with multiple adverse events within a primary system organ class is only counted once towards the total of the primary system organ class.

Vital signs

All vital signs data will be listed by treatment group, subject, and visit/time and if ranges are available, abnormalities (and relevant orthostatic changes) will be flagged. Summary statistics will be provided by treatment and visit/time.

12-lead ECG

PR, QRS, QT, QTcF, and RR intervals will be obtained from 12-lead ECGs for each subject during the study. ECG data will be read and interpreted (centrally/locally).

All ECG data will be listed by treatment group, subject and visit/time, abnormalities will be flagged. Summary statistics will be provided by treatment and visit/time.

Clinical laboratory evaluations

All laboratory data will be listed by treatment group, subject, and visit/time and if normal ranges are available abnormalities will be flagged. Summary statistics will be provided by treatment and visit/time. Shift tables using the low/normal/high/ (low and high) classification will be used to compare baseline to the worst on-treatment value.

Grading of laboratory values will be assigned programmatically as per NCI Common Terminology Criteria for Adverse Events (CTCAE) version 5.0 or current version. The calculation of CTCAE grades will be based on the observed laboratory values only, clinical assessments will not be taken into account.

CTCAE Grade 0 will be assigned for all non-missing values not graded as 1 or higher. Grade 5 will not be used.

For laboratory tests where grades are not defined by CTCAE, results will be categorized as low/normal/high based on laboratory normal ranges.

The following summaries will be generated separately for hematology, and biochemistry tests:

- 1. Listing of all laboratory data with values flagged to show the corresponding CTCAE grades if applicable and the classifications relative to the laboratory normal ranges
- 2. For laboratory tests where grades are defined by CTCAE,
- 3. Worst post-baseline CTCAE grade (regardless of the baseline status). Each subject will be counted only once for the worst grade observed post-baseline.
- 4. Shift tables using CTCAE grades to compare baseline to the worst on-treatment value
- 5. For laboratory tests where grades are not defined by CTCAE,

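### The SAP's AESI tables apply grade floors that the protocol's AESI definition does not set for cardiovascular/electrolyte events or for haematological events with clinical consequences, and the SAP does not declare the change

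*SAP*

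**What the plan says.** Protocol 10.1.5 names four AESI categories: haematotoxicity, secondary haematological malignancies, nephrotoxicity, and cardiovascular and electrolyte disorders. Haematotoxicity has two limbs. The first goes by grade: it is "defined as Grade 2 or higher thrombocytopenia, or Grade 3 or 4 of anaemia, leuko-/neutropenia are considered dose-modifying toxicities". The second goes by consequence: "Haematological toxicities regardless of severity must be reported as AESI if accompanied by clinical consequences", with infection, bleeding, and otherwise unexplained dyspnoea or fatigue as the consequences meant. The cardiovascular and electrolyte category rests on clinical significance. It covers blood pressure, heart rate and ECG changes close in time to Lutathera or amino-acid administration, and "any clinically significant event of hyperkalemia or hypokalemia must be reported as AESI". No grade threshold is given.

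Protocol 12.5.3 sets the analysis: "subjects with AESI/related to identified and potential risks (see Section 10.1) will be summarized by treatment".

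SAP 2.8.1.1 notes that "Certain AESIs in this study are flagged in the eCRF by the investigator within the adverse event form", re-derives the groups from MedDRA queries held in the electronic Case Retrieval Sheet (eCRS), and adds grade rules in Table 2.8-1. For thrombocytopenia and then the other haematotoxicities the rule is "only include Grade >=2; for others only include Grade >=3"; for the cardiovascular and electrolyte group it is "only include Grade >=3". The section then states: "The re-derived AESI groupings using eCRS will be used in the analyses". SAP Section 4, on changes to the protocol's analyses, reports none.

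**The concern.** The protocol's analysis section sends the reader to Section 10.1 for what an AESI is. The SAP tabulates a narrower set in two of the four categories, specifies no table based on the investigator's flag, and does not tell the reader that the two sets differ. Anyone who reads an AESI incidence in the study report against Protocol 10.1.5 would take it to include events that were filtered out.

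The stake is the transparency and completeness of a safety summary for the risks that the protocol links to Lutathera and the amino-acid infusion. The AESI tables are where those risks are drawn together by seriousness, relationship and action taken, and they are the only place where time to first occurrence is estimated. The protocol lists hypokalaemia among the common side effects of Lutathera (Section 1.1), so lower-grade electrolyte events are not a remote possibility.

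**Working it through.** There is no figure to reproduce. The check sets Protocol 10.1.5 beside SAP Table 2.8-1, one kind of event at a time.

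| Event | AESI in Protocol 10.1.5 | In the SAP's AESI tables |
|---|---|---|
| a. Thrombocytopenia, Grade 2 or higher | yes | yes |
| b. Thrombocytopenia, Grade 1, with bleeding or purpura | yes | no |
| c. Anaemia or leuko-/neutropenia, Grade 3 or 4 | yes | yes |
| d. Anaemia or leuko-/neutro-/lymphopenia, Grade 1 or 2, with infection or unexplained dyspnoea/fatigue | yes | no |
| e. Clinically significant blood pressure, heart rate or ECG change, Grade 1 or 2, close to administration | yes | no |
| f. Clinically significant hyper- or hypokalaemia below Grade 3 | yes | no |
| g. Secondary haematological malignancies; nephrotoxicity | yes | yes, no grade filter |

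Rows a and c show that the haematology cut-offs reproduce the protocol's first limb. The haematology gap is confined to rows b and d, the consequence limb. For cardiovascular and electrolyte events (rows e and f) the whole floor is the SAP's addition.

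As an illustration of row f, the laboratory grading in SAP 5.3 puts potassium above 5.5 and up to 6.0 mmol/L at Grade 2, and potassium from 3.0 mmol/L up to the lower limit of normal at Grade 1. A clinically significant event in either band is an AESI under the protocol. If its AE record carried the same grade, it would fall below the SAP's floor. SAP 5.3 assigns these grades from laboratory values alone, so the grade on the AE record may differ.

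What happens to a patient whose only events are in rows b, d, e or f:

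- *AESI summaries* (randomized period and overall study period): not counted.
- *Time to first AESI, randomized period*: the censoring rules in SAP 2.8.1.1 treat the patient as having reported no AESI, so the patient is censored as event-free. The whole-study version covers only secondary haematological malignancies and nephrotoxicity and is unaffected.
- *General AE reporting* (SAP 2.8.1): the events are listed and, if treatment-emergent, counted by system organ class and preferred term. An AESI recorded in follow-up that is not treatment-emergent appears only in listings if it is below the floor.

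**The case against.** The strongest reply is that little is lost. All AEs are listed, and treatment-emergent ones are tabulated by arm, with tables by relationship, seriousness, discontinuation, dose change and additional therapy. SAP 2.8.3 gives worst-grade and shift tables for haematology and biochemistry, including potassium, and SAP 2.8.4 summarises notable ECG and vital-sign values. Protocol 10.1.5 is written mainly as a reporting rule for investigators, and aligning AESI groups across a development programme is a legitimate aim. All of this stands, and it limits the point to the AESI outputs. It does not remove the point: Protocol 12.5.3 makes Section 10.1 the reference for the AESI summary. The SAP's change history mentions an update of the AESI grouping but does not present it as a departure from the protocol.

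Four stronger readings are tempting, and the documents do not support them.

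- *AESI incidence will be understated overall.* Re-derivation also drops the investigator's judgement of clinical significance and timing, so it can add qualifying-grade events that nobody flagged. The net direction is unknown.
- *The loss falls mainly on the Lutathera arm.* The cardiovascular limb is tied to infusions that only that arm receives in the randomized period, but electrolyte events can arise in either arm and no counts are given.
- *AESI leading to dose change will be understated.* Protocol Table 6-4 acts mostly at the same grades as the SAP's floors, so this effect is not shown.
- *The SAP calls the filter conservative.* That word is attached to the MedDRA re-derivation; the grade rules are introduced separately.

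SAP 5.2 allows a three-point severity scale for terms absent from CTCAE, and 2.8.1.1 does not say how the floor applies to it or to a missing grade. That is an unspecified edge case and not a demonstrated failure.

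**Conclusion.** The mismatch is real and can be read directly from the two texts: an undeclared Grade 3 floor on one whole AESI category, and the loss of the consequence limb in another. Its reach is the AESI summaries and the randomized-period time-to-first-AESI analysis. These are descriptive outputs, and no hypothesis test or error rate depends on them. The number of patients affected cannot be derived.

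The conclusion assumes that the cross-reference in Protocol 12.5.3 carries the Section 10.1.5 definition into the analysis. It also assumes that the eCRS, which is not in the documents, does not bring the lower-grade events back by another route. An infection or haemorrhage could enter an AESI group in its own right only if the eCRS includes the term and the event meets the grade rule. The mismatch should be corrected, but it is not evidence that the safety reporting as a whole is deficient.

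**What to change.** Keep the eCRS-based, grade-filtered tables for programme alignment. Add the following to SAP 2.8.1.1, for both arms:

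1. For the cardiovascular/electrolyte category, an all-grade eCRS-based summary and an all-grade time to first occurrence.
2. A row or supplementary table counting investigator-flagged AESI, including lower-grade haematological events with clinical consequences.

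In SAP Section 4, declare the grade filter and give its rationale.

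The flagged count should sit beside the eCRS tables and not replace them. The trial is open-label, the SAP says that only certain AESIs are flagged, and the cardiovascular flag depends partly on closeness to an infusion that control patients do not receive in the randomized period. The eCRS tables apply the same search to both arms, whereas the flag carries the clinical judgement that the protocol's definition requires.

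The cost is SAP wording and a few extra rows or tables, from data already collected. Reported AESI rates may look less favourable.
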